8. RANDOMIZATION

Study participants will be randomized to the treated arm (mirabegron 50 mg orally once every 24 hours starting immediately) or placebo in a 1:1 ratio using a randomized block design, stratified by stone size (≤ 5 mm versus > 5 mm) and location (upper versus lower ureter). The randomization will be implemented through a database with software designed by the Director of Research Informatics at the Baylor College of Medicine's (BCM) Dan Duncan Institute of Clinical and Translational Research. It will be a HIPPA-compliant secure database accessible via internet.

Each randomly assigned participant will be given 60 capsules of trial medication (over-encapsulated mirabegron or placebo) supplied by Astellas Pharm US, Inc. and dispensed by the Harris Health System Pharmacy. Both Astellas Pharm US, Inc. and Harris Health Pharmacy will have no further involvement in the trial, ensuring that participants, clinicians, and trial personnel remained unaware of the allocated group.

Justification:

Two decades ago, the first randomized trial demonstrating the potential efficacy of a calcium channel blocker (nifedipine) for medical expulsive therapy of ureteral stones was performed.³ Subsequently, tamsulosin, a selective alpha-1a antagonist, has also been demonstrated as a potentially useful agent for MET in randomized trials.⁴ Over the past decade, off-label MET has become more commonplace. However, the strength of findings from randomized trials is weak due to variability in quality and power of study design.

In 2015, a large multi-center randomized placebo-controlled trial (SUSPEND Trial) included 1167 patients and compared the efficacy of nifedipine and tamsulosin for the reduction in surgical therapy in patients passing ureteral stones within 4 weeks after randomization.⁵ This trial demonstrated that both nifedipine and tamsulosin were ineffective for MET and were associated with an increase in adverse effects compared to placebo. These findings suggest that current off-label therapy with calcium-channel blockers and alpha-blockers may be ineffective and inappropriate. Because ureteral stones remain an important and expensive medical problem, identification of other potential agents for MET may reduce the frequency of serious complications and necessity of surgical intervention as well as improve patient-centered outcomes.

9. PROCEDURES

Visit 1 – Emergency Department

In the ED, the subjects will receive a full history and physical, blood tests (including CBC and BMP), urinalysis and culture, urine pregnancy test, CT scan or Ultrasound/KUB of the abdomen

and pelvis, and KUB as part of standard of care for ureteral colic. The radiology department will note on all imaging the largest diameter of the stone and the Hounsfield units. Research study staff will screen potential subjects in the ED by reviewing their charts and will obtain written and verbal consent (in Spanish when necessary) from subjects who meet all inclusion and exclusion criteria. Baseline data, including demographics, medical and surgical history, and current medications, will be collected before randomization.

Each subject will be assigned a unique, consecutive three-digit identification number (i.e., 001, 002...). The study number will be utilized for identification of the subject throughout the study. The clinical study coordinator of the trial will maintain the code that links the name of the participant to their study identification number. The study coordinator will maintain the code in a secured cabinet and the code will be kept confidential. Only the clinical study coordinator and Principal Investigator (PI) can access and view the codes.

Subjects will be asked to complete the Wong-Baker FACES pain scale (available with validated Spanish translation as well). Subjects will be discharged from the ED with a (1) 60 day prescription for the study drug (mirabegron or placebo) (2) urine strainer (3) 60 day log for recording medication adherence, narcotic/analgesic usage, and ureteral pain. Subjects will be instructed to take one pill per day beginning immediately and continuing until they have completed all pills or until they have been instructed to discontinue by the study staff.

Subjects will be provided instructions for use of the urine strainer and collection of any stone or stones that may be passed. They will be instructed to bring any stones that have been passed to the next clinic visit.

Subjects will be informed that they may also discontinue the study drug at any time if they would like to drop out of the trial and they may do so by contacting [name] or designee. Subjects will be informed to contact [name] or designee if they believe that they have passed their ureteral stone before discontinuing therapy. Subjects will be told to bring their medication bottles when they return to the clinic.

In the event that a subject has additional pain, discomfort, or other symptoms that may be related to their ureteral stone they may follow-up for an unscheduled visit to either the emergency department or the Urology clinic. The subject will be treated according to standard of care and information regarding their visit will be collected. If the subject must undergo an emergent procedure for their stone they will be determined to have failed therapy but will remain in the study to evaluate the study drug to reduce stent pain. Subjects that fail therapy early will undergo Visit 3 and will be evaluated at Visit 4 for the removal of their stent. Subjects will remain in the study for all outcome measurements if they do not require surgical intervention.

Interim Phone Follow-up #1 – (7 Days ± 3 days post-Visit 1)

The research study staff will contact the subject by phone approximately 7 days after Visit 1. Research staff will assess ureteral pain, medication/strainer compliance, and adverse events. Research staff will also identify whether or not the subject subjectively or objectively has passed their ureteral stone. The research staff will also answer any questions that the subject may have during this follow-up event.

Interim Phone Follow-up #2 – (21 Days ± 3 days post-Visit 1)

The research study staff will contact the subject by phone approximately 21 days after Visit 1. Research staff will assess ureteral pain, medication/strainer compliance, and adverse events. Research staff will also identify whether or not the subject subjectively or objectively has passed their ureteral stone. The research staff will also answer any questions that the subject may have during this follow-up event. The research staff will also remind the subjects to bring in their medication bottles to Visit 2 (see below).

Visit 2 – Urology Clinic (30 days ± 5 days post-Visit 1)

Subjects will follow-up in the Harris Health Urology Clinic approximately 30 days after Visit 1. Subjects will provide a blood sample for a CBC, BMP, coagulation studies (PT/INR/PTT), a urine sample for a urinalysis and culture, urine pregnancy test, and have their blood pressure taken, as per standard of care. Subjects will also undergo a CT or KUB plus renal ultrasound at the Harris Health Radiology Department to radiologically identify the status of their ureteral stone, as per standard of care.

| In the Urology Clinic, staff will perform a brief history and physical, review clinical imaging, observe any stones that the subject has collected, and determine whether or not the subject has passed their ureteral stone. Clinical and research staff will assess blood pressure, ureteral pain, pain medication and pain score log compliance, medication/strainer compliance, and adverse events using the adverse event checklist. Subjects will be asked to bring in their medication bottles at this visit to assess medication compliance. Subjects with persistent ureteral stones will be scheduled for ureteroscopy with laser lithotripsy and ureteral stent placement. These subjects will continue the study drug and strain their urine. Subjects will be provided additional study drug if necessary and instructed to continue until Visit 4, regardless of if they believe they passed their stone or not. They will be asked to bring the study drug bottle and any collected stones upon their return to Visit 3.

Subjects who have passed their stone will discontinue the study drug and exit the study.

Visit 3 – Ureteroscopy (14 days ± 5 days post-Visit 2)

Subjects who have failed the expectant management period as determined on Visit 2 will undergo ureteroscopy with laser lithotripsy approximately 14 days after Visit 2. Blood pressure will be checked prior to the procedure. Stone fragments will be collected for composition analysis. All subjects will be stented using the preferred 6-French Boston Scientific Contour Injection Ureteral Stent Set that has been appropriately sized for each patient. If this particular catheter cannot be used, any 6-French catheter is preferred, but any ureteral catheter may be utilized during this visit. The string will not be removed from the ureteral stent to facilitate easier removal later. In subjects for whom the ureteroscope cannot successfully be passed into the ureter after reasonable attempts, the surgeon will place a ureteral stent and the subject will remain on the trial until their ureteral stent has been in 1 week or until Visit 4. Subjects will receive 10 days of ciprofloxacin, Tylenol #3, phenazopyridine, per standard of care. Subjects will not be prescribed alpha-adrenergic blockers or anticholinergics.

Clinical and research staff will assess blood pressure, ureteral pain, pain medication and pain

score log compliance, medication/strainer compliance, and adverse events using the adverse event checklist.

They will be asked to bring the study drug bottle upon their return to the clinic at Visit 4. It is possible that some patients will pass their stone between visit 2 and visit 3. If the patient has physically seen the stone pass or has collected the stone, they will exit the study; otherwise, they will proceed with a diagnostic versus therapeutic ureteroscopy with stent placement.

Visit 4 – Removal of Ureteral Stent (7 days ± 3 days post- Visit 3)

Subjects will return the Harris Health Urology Clinic approximately 7 days after ureteroscopy to remove their ureteral stent. In the Urology Clinic, staff will perform a brief history and physical, including blood pressure, per standard of care. Subjects will complete the USSQ. Stent pain, medication compliance, and medication-related adverse events, if any, will be assessed. Subjects will be asked to return any unused study drug and the study drug bottle at this visit. For subjects in whom the ureteroscope could not be passed and a stent was left in place, this visit will be a return to the operating room for completion ureteroscopy or stent removal, as clinically indicated.

Early Completion of the Trial Period

Subjects will be asked to call the study staff if they believe that they have passed their ureteral stone during the expectant management period or before ureteroscopy. Subjects that have objectively passed their stone will be asked to bring stone fragments for composition analysis. Subjects that have subjectively passed their stones will be asked to continue on their study medication until they can undergo a CT or KUB plus renal ultrasound and be interviewed in person by the clinical staff to determine stone passage. If a subject completes the trial before Visit 4, they will be asked to return any unused study drug.

Protocol Exceptions

Under the circumstance that any clinic visit cannot be made within the given timeframe due to system or subject issues unrelated to the study staff, the PI can review each case on an individual basis. If the PI determines that standard of care is ongoing, the subject may remain on the study. Under the circumstance that this may delay time to completion, the PI may extend study drug until completion of the trial. Extension of the study drug may continue in continuation with the initial 60 day dose or may be restarted after a period of drug cessation. This extension is not to exceed 60 additional days.

Monitoring of Adverse Events

Safety outcomes will be reported when they happened (via the case report form, patient questionnaires, and patient and clinician report). Suspected serious adverse events will be graded at site by the principal investigator. Safety events will be monitored by Astellas research ethics committee, and MHRA. Reporting of unanticipated problems will be in accordance to the current IRB guidelines and FDA regulations. An adverse event log will be maintained at the clinical site. The logs will be tabulated into a master log and submitted with each annual IRB renewal report.

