6. ELIGIBILITY CRITERIA

A. Inclusion

Subjects are eligible to be included in the study only if they meet all of the following criteria and provide signed informed consent at Visit 1.

- 1) Males and females age 18-70 years of age
- 2) Resident of Harris County
- 3) Single unilateral ureteral calculus 4 to 10 mm visible on CT scan or

- 4) Ability to tolerate oral fluids and oral pain medication
- 5) Able to make informed medical decisions regarding consent
- 6) Willingness to follow-up in the Urology Clinic in approximately 30 days
- 7) Willing to undergo ureteroscopic extraction should the stone not pass in this time period

B. Exclusion

Subjects will be excluded from the study if they meet any of the following criteria:

- 1) Adults unable to consent
- 2) Age less than 18
- 3) Solitary kidney
- 4) Horseshoe kidney
- 5) On immunosuppressant therapy
- 6) On digoxin
- 7) Uncontrolled hypertension (SBP > 170, DBP > 110)
- 8) Allergy to mirabegron
- 9) Current calcium antagonist or corticosteroid or alpha-adrenergic antagonist usage
- 10) Patients already taking a beta-adrenergic agonist medication
- 11) Patients taking thordiazine, flecainide, or propafenone (narrow CYP2D6 therapeutic index)
- 12) Renal insufficiency (GFR less than 45)
- 13) Patients with Childs B and C liver failure
- 14) Signs of infection
 - i. Temperature greater than 38C
 - ii. Circulating white blood count $>15,000 \times 10^9/L$
 - iii. Urinalysis with any of the following positive:
 - a) Positive nitrites
 - b) Positive urine culture (defined as a single isolated bacterial species population of greater than 100,000 CFU)
- 15) Patients with chronic pain already undergoing treatment with narcotic medications
- 16) Pregnant women and nursing mothers
- 17) Prisoners
- 18) No working phone number

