PREGNANCY: It is possible that the medicines used in this study could injure a fetus if the subject or partner becomes pregnant while taking them. Because of the potential risks involved, the subject or partner should not become pregnant while you are participating in this study.

If subject is sexually active or become sexually active and can get pregnant or can get the partner pregnant, the subject must agree to use one of the following forms of birth control every time the subject has sex from now until 3 months after stopping the study drug:

- * oral contraceptives ("the pill"),
- * intrauterine devices (IUDs),
- * contraceptive implants under the skin, or contraceptive injections,

* condoms with foam.

Should pregnancy occur while on this study, the subject must immediately notify the study personnel.

The investigator will assist in finding appropriate medical care. The investigator also may ask to be allowed to continue getting information about the pregnancy. The subject can choose not to provide this information.

- B.** Blood Draw: Inserting needles into veins for collecting blood may be uncomfortable. Risks include slight bruising at the puncture site, fainting, the formation of a small blood clot or swelling of the vein and surrounding tissue, bleeding from the site, and the remote possibility of infection at the site of the needle puncture. Fainting is usually harmless, of short duration, and typically produces feelings of weakness, sweating, slowing of the heart rate and an abnormal decrease in blood pressure. Care will be taken to avoid these complications.
- C.** Blood Pressure: Subjects may feel a slight discomfort while the band on the arm is tightened in order to take the reading.

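### The pregnancy test is repeated at Visit 2, but subjects with a persistent stone are told to continue study drug whatever the result, and no visible text makes pregnancy a mandatory drug stop

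*Combined protocol and SAP*

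**What the plan says.** **Visit 2 (Section 9).** The tests at about day 30 include "urine pregnancy test, and have their blood pressure taken, as per standard of care". Subjects are then divided by whether the stone has passed. Those who have passed it stop drug and leave the study. Of those with a persistent stone the text says "These subjects will continue the study drug and strain their urine", and then "Subjects will be provided additional study drug if necessary and instructed to continue until Visit 4".

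**Pregnancy elsewhere in the protocol.** Section 6 excludes "Pregnant women and nursing mothers" (exclusion 16). Section 15 states "It is possible that the medicines used in this study could injure a fetus" and requires contraception "from now until 3 months after stopping the study drug". If pregnancy happens anyway, Section 15 says "Should pregnancy occur while on this study, the subject must immediately notify the study personnel" and "The investigator will assist in finding appropriate medical care". It adds that the investigator may ask for continuing information about the pregnancy.

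**Stopping and extending drug.** Visit 1 in Section 9 tells subjects to take one capsule daily until the supply is finished or study staff tell them to stop. Section 17 lists five grounds, A to E, for discontinuing a subject from the study; pregnancy is not named. Protocol Exceptions in Section 9 lets the PI extend or restart drug for up to 60 more days when visits are delayed. Appendix A marks the pregnancy test at Visits 1 and 2 only.

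**The concern.** A repeat safety test should have a stated consequence. Here the protocol writes a rule for continuing drug at the same visit, but bases it only on the stone. Read literally, a woman with a persistent stone and a positive test falls under the instruction to continue, although she could not have been enrolled with that result and the protocol itself names a possible fetal hazard.

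What is at stake is subject and fetal safety, and consistent handling of such a case. Without a written rule, staff must decide for themselves whether to stop drug, whether to wait for confirmation, and whether the subject stays in follow-up.

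**Working it through.** No power, sample-size or error-rate figure bears on this point. The check sets the relevant text side by side and adds up the visit intervals.

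**Step 1. Is there a pregnancy stop rule anywhere in the visible text?**

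| Place | What it provides | Mandatory drug stop for pregnancy? |
|---|---|---|
| Section 6, exclusion 16 | Bars pregnant women at entry | No; governs enrolment only |
| Section 9, Visit 1 | Staff may tell a subject to stop drug | No; no trigger given |
| Section 9, Visit 2 | Test repeated; dosing decided by stone status | No |
| Section 9, Protocol Exceptions | Extension or restart after PI review | No; no test required first |
| Section 15, Pregnancy | Contraception, notification, help finding care | No |
| Section 17 A | Unacceptable adverse event attributed to study drug | No; a pregnancy need not be one |
| Section 17 B | Subject asks to withdraw | No; her choice |
| Section 17 C | Need for a prohibited concomitant medication | No; different subject matter |
| Section 17 D | PI judges it best for the subject | Could apply, but discretionary |
| Section 17 E | Significant non-compliance | Only if required contraception was not used; contraception can fail in a compliant subject |
| Appendix A | Pregnancy test at Visits 1 and 2 | No; no later test |

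No row requires drug to stop because of pregnancy. Two rows allow it by judgement: the staff instruction at Visit 1 and Section 17 D.

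**Step 2. How much dosing does the Visit 2 instruction cover?**

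Inputs from Section 9: Visit 3 is 14 ± 5 days after Visit 2, and Visit 4 is 7 ± 3 days after Visit 3.

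- Nominal: 14 + 7 = 21 days
- Shortest: (14 − 5) + (7 − 3) = 9 + 4 = 13 days
- Longest: (14 + 5) + (7 + 3) = 19 + 10 = 29 days

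Appendix A agrees on the nominal figure: day 51 − day 30 = 21 days.

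**Step 3. Extension.** Protocol Exceptions can add up to 60 days, after individual PI review, with no scheduled pregnancy test after Visit 2.

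**The case against.** The strongest reply is that no competent team would knowingly keep a pregnant subject on drug. Notification of pregnancy is immediate and mandatory, staff can tell a subject to stop, and Section 17 D removes a subject once the PI judges that best for her. Section 9 also asks subjects to bring their medication bottles to Visit 2 for a compliance check, so leftover capsules could be collected there. The pregnancy test is one of several standard-of-care tests at that visit, and no action rule is written there for the others. Finally, the consent pages were removed before review and may contain a stop instruction.

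Most of this stands, and it limits the practical risk. A reader might infer that the protocol directs staff to dose pregnant women, or that capsules already dispensed would carry dosing on unchecked. The documents do not support either: the gap is silence about a test result, there are routes to stopping, and the bottles should be in clinic.

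Two things remain. The routes to stopping are discretionary, while the continuation instruction is not. The comparison with the other Visit 2 tests is also incomplete, because the protocol makes pregnancy an entry exclusion, attaches a named fetal hazard to it, and requires contraception throughout dosing and for three months afterwards. A positive result therefore bears directly on whether drug should continue.

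**Conclusion.** The point holds as a gap in the protocol wording. The Visit 2 continuation rule takes no account of the pregnancy test done at that visit, and no visible text makes pregnancy a mandatory reason to stop drug. The instruction covers a nominal 21 days of dosing (13 to 29), and any extension up to 60 more.

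The number of subjects is not given and is probably very small: women who can conceive, whose stone persists, and who test positive. With 1:1 allocation about half of them would be on placebo.

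A reader might also infer damage to the trial's results. The documents do not support that. The primary 30-day endpoint is unaffected, and any effect on the stent-pain comparison would involve at most an occasional subject.

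The conclusion assumes that no unseen page supplies the missing rule. A stop instruction in the consent form cannot be excluded, but the Visit 2 text that staff follow should still agree with it. This is a cheap safety improvement, not a flaw in the design or analysis.

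**What to change.** 1. **Section 9, Visit 2.** Make continuation conditional: subjects with a persistent stone continue study drug only if the Visit 2 pregnancy test, where applicable, is negative. On a positive result drug is held; if pregnancy is confirmed, drug is stopped and remaining capsules are collected.
2. **Section 17.** Add confirmed pregnancy at any time as a reason to stop study drug, stated separately from withdrawal from the study. Outcomes are then still collected, including the stent symptom questionnaire (USSQ) at Visit 4 if a stent is placed.
3. **Section 9, Protocol Exceptions.** Apply the same stop to any PI extension or restart, and require a negative urine pregnancy test first.

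**Cost.** A short wording amendment with institutional review board approval, using a test already scheduled and adding no visit. The only new procedure is one urine test in extension or restart cases. An occasional subject will be off drug before the stent-pain assessment. A false positive could interrupt dosing, which is why the text should hold drug first and stop it only on confirmation.

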15. RISKS

There are risks to any medication. However, mirabegron is a FDA-approved medication and has passed rigorous trials for safety.

- A. Mirabegron:** Mirabegron is contraindicated in patients who have known hypersensitivity reactions to mirabegron or any component of the tablet. Mirabegron can increase blood pressure. Periodic blood pressure determinations are

recommended, especially in hypertensive patients. Mirabegron is not recommended for use in severe uncontrolled hypertensive patients (defined as systolic blood pressure ≥ 180 mm Hg and/or diastolic blood pressure ≥ 110 mm Hg).

Urinary retention in patients with bladder outlet obstruction (BOO) and in patients taking antimuscarinic medications for the treatment of OAB has been reported in post-marketing experience in patients taking mirabegron. A controlled clinical safety study in patients with BOO did not demonstrate increased urinary retention in Mirabegron patients; however, Mirabegron should be administered with caution to patients with clinically significant BOO. Mirabegron should also be administered with caution to patients taking antimuscarinic medications for the treatment of OAB.

Angioedema of the face, lips, tongue and/or larynx has been reported with Mirabegron. In some cases angioedema occurred after the first dose. Cases of angioedema have been reported to occur hours after the first dose or after multiple doses. Angioedema associated with upper airway swelling may be life threatening. If involvement of the tongue, hypopharynx, or larynx occurs, promptly discontinue Mirabegron and initiate appropriate therapy and/or measures necessary to ensure a patent airway.

Since Mirabegron is a moderate CYP2D6 inhibitor, the systemic exposure to CYP2D6 substrates such as metoprolol and desipramine is increased when co-administered with Mirabegron. Therefore, appropriate monitoring and dose adjustment may be necessary, especially with narrow therapeutic index drugs metabolized by CYP2D6, such as thioridazine, flecainide, and propafenone.

Most commonly reported adverse reactions over 2% and greater than with placebo) were hypertension, nasopharyngitis, urinary tract infection and headache.

Subjects will be monitored carefully for such side effects and should the subject feel uncomfortable continuing treatment, he will be allowed to discontinue participation in the study.

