16. ASSESSMENT OF SAFETY

A. Adverse Events Reporting

All adverse event (Severe Adverse Event (SAE), Unanticipated Event (UAE), or Adverse Event (AE) will be assessed by the Principal Investigator using the BCM PI Determination form. The IRB will be notified according to current rules, regulations, and procedures.

B. Serious Adverse Event Reporting

Within 24 hours of awareness of a serious adverse event, whether or not related to the study drug, the Investigator will complete and submit a Medwatch 3500A Form to FDA, containing all required information (reference 21 CFR 312.32). The Investigator will submit a copy of this MedWatch 3500A form to Astellas by either e-mail or fax, within the same timeframe. If submission of this SAE to FDA or Astellas or is not possible within 24 hours, the Investigator's local drug safety contact (IRB, etc.) should be informed by phone.

The SAE documentation, including the Medwatch 3500A Form and available source records should be emailed or faxed to:

Astellas Pharma Global Pharmacovigilance – United States
Email: [contact]
[contact]

The following minimum information is required:

- Study number/IIT regulatory identifier
- Subject number, sex and age
- The date of report
- A description of the SAE (event, seriousness of the event)
- Causal relationship to the study drug

Follow-up information for the event should be sent promptly (within 7 days) as necessary.

C. Additional safety analyses will be conducted in the safety population, defined as all subjects who receive at least one treatment with study drug.

Safety and tolerability will be assessed by evaluating physical, clinical laboratory tests, and reported AEs.

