APPENDIX A: SCHEDULE OF EVENTS

Highlighted events are considered standard of care.

Events/Time	Visit 1 Screening/ Randomization (D1)	Interim Follow-up #1 (D7 ± 3 days) Phone Call	Interim Follow-up #2 (D21 ± 3 days) Phone Call	Visit 2 Urology Clinic (D30 ± 5 days)	Visit 3 Ureteroscopy (D44 ± 3 days)	Visit 4 Removal of Ureteral Stent (D51 ± 3 days)
Complete History/Physical	X ¹					
Office Visit w/brief H&P				X		X
Blood Pressure	X ¹			X	X	X
Ureteroscopy, laser lithotripsy, stent placement					X	
Phlebotomy	X ¹			X		
CBC	X ¹			X		
BMP	X ¹			X		
Coagulation Panel				X		
Urine Collection						
Urinalysis	X ¹			X		
Culture	X ¹			X		
Pregnancy test	X ¹			X		
CT	X ¹			X ²		
KUB	X ¹					
KUB plus ultrasound				X ²		
Stone Analysis					X	
Randomization	X					
Mirabegron/Placebo Dispense	X					
Urine Strainer	X ¹					
Ciprofloxacin, Tyleynol3, phenazopyridine					X	
Medication Accountability		X	X	X		X
Straining Accountability		X	X	X		
Wong-Baker FACES Pain Rating Scale, Narcotics Diary	X	X	X	X		X
USSQ						X
Informed Consent	X					
Adverse Events		X	X	X	X	X
Review Concomitant Meds	X			X		

¹May be done prior to enrollment into study

²May be used instead of CT

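### The Visit 4 text limits adverse events to medication-related ones, against Appendix A and Section 16A, so non-serious events can be screened out before they are recorded

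*Combined protocol and SAP*

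**What the plan says.** Section 9 describes adverse event collection contact by contact.

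- **Both phone calls:** "Research staff will assess ureteral pain, medication/strainer compliance, and adverse events".
- **Visits 2 and 3:** staff assess "medication/strainer compliance, and adverse events using the adverse event checklist".
- **Visit 4 (stent removal):** "Stent pain, medication compliance, and medication-related adverse events, if any, will be assessed". No checklist is named.

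Three other places carry no such limit.

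- The adverse event row of Appendix A reads "Adverse Events X X X X X": both calls and Visits 2, 3 and 4, with no footnote at Visit 4.
- Section 16A states: "All adverse event (Severe Adverse Event (SAE), Unanticipated Event (UAE), or Adverse Event (AE) will be assessed by the Principal Investigator", on an existing determination form.
- Section 9, under monitoring of adverse events, has safety outcomes reported as they occur and a site log kept.

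Section 16B requires serious events to be reported regardless of their relation to study drug. Section 15 says the most commonly reported reactions to mirabegron "were hypertension, nasopharyngitis, urinary tract infection and headache", and separately mentions urinary retention and angioedema. Section 7 keeps subjects on study drug while the stent is in place. Section 10 and Appendix A schedule blood and urine tests at Visit 1 and the 30-day visit only.

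**The concern.** Visit 4 is the only contact whose text asks staff to decide on cause before they assess an event. It is also where that decision is hardest. Every subject there has had recent instrumentation of the ureter and carries a stent, so a urinary event has a ready explanation other than the drug. An event set aside at that point may never reach the principal investigator, whose task under Section 16A is to assess all of them.

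There is no later scheduled contact to recover a missed event, and no urinalysis or culture at Visit 4 to detect an infection independently. Stent-associated pain is a secondary objective, so any claim of benefit in this period needs a safety record collected by the same rule as the rest of the trial.

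**Working it through.** **1. The instructions side by side.**

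| Contact | Limited to drug-related events? | Checklist named? | Marked in Appendix A? |
|---|---|---|---|
| Phone call 1 | No | No | Yes |
| Phone call 2 | No | No | Yes |
| Visit 2 | No | Yes | Yes |
| Visit 3 | No | Yes | Yes |
| Visit 4 | Yes | No | Yes |

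The causality limit is unique to Visit 4. The missing checklist is not, since the phone calls name none either. The Visit 4 sentence cannot be squared with Appendix A and Section 16A as written.

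**2. Which events are exposed.** Serious events are protected by Section 16B. Blood pressure is measured at Visit 4 whatever staff think of cause, which covers hypertension. Nasopharyngitis, headache and angioedema do not resemble stent effects. That leaves non-serious urinary tract infection and, less so, retention. Their overlap with stent effects is a clinical inference; the documents describe no stent effect beyond pain.

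**3. How many subjects.** The plan gives no figure for adverse event collection, so its sample size inputs (Section 11) are used: 50% passage on placebo, a 0.30 difference (hence 80% on mirabegron), 45 per group, 104 enrolled. These reproduce: the continuity-corrected two-proportion formula gives 45 per group, exact Fisher power at 45 is 0.815, and 90 × 1.15 = 103.5, rounded up to 104. Assume every non-passer reaches Visit 4.

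- 52 per arm (104 ÷ 2): placebo 52 × 0.50 = 26; mirabegron 52 × 0.20 = 10.4; total 36.4, and 36.4 ÷ 104 = 35%.
- 45 per arm: placebo 45 × 0.50 = 22.5; mirabegron 45 × 0.20 = 9; total 31.5.
- If mirabegron does nothing, each arm has 22.5 (of 45) or 26 (of 52).

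The first line ignores attrition, and all lines ignore subjects who pass the stone between Visits 2 and 3 and leave the study. With 9 to 10.4 subjects on mirabegron, one unrecorded event moves that arm's stent-period rate by 1 ÷ 10.4 = 9.6 to 1 ÷ 9 = 11.1 percentage points.

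**4. What filtering does to a comparison.** Let a fraction *s* of events be recorded in both arms, with true risks p(M) and p(P). The observed risk difference is s × [p(M) − p(P)]. For assumed *s* of 0.75, 0.50 and 0.25 it is three quarters, a half and a quarter of the truth. The ratio is unchanged in expectation.

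**5. A separate matter: pooling the two periods.** Section 16C defines one safety population and no split by period, yet half the placebo arm and a fifth of the mirabegron arm would enter the stent period under the plan's rates. As an illustration on assumed rates, let infection be 5% (placebo) and 10% (mirabegron) in the expectant period and x% after stenting in either arm, all fully recorded and summed with overlap ignored. The pooled difference is (10 + 0.2x) − (5 + 0.5x) = 5 − 0.3x points: 5 at x = 0, 2 at x = 10, and −1 at x = 20. This comes from unequal entry to surgery, not from the Visit 4 wording.

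**The case against.** The strongest reply is that this is a loose phrase and not a rule. Appendix A, Section 16A and the site log all call for adverse events at or through Visit 4 without a causality limit, and Visit 4 includes a history, an examination and blood pressure. A careful coordinator would record everything. That stands as far as it goes: loss of events is possible, not planned. But the visit text is what staff follow on the day, and nothing says which text prevails.

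Several stronger readings are tempting, and the documents do not support them.

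- *A reader might infer that the plan collects only drug-related events in the stent period.* It does not, for the reasons just given, and serious events are reported regardless of cause.
- *A reader might infer that all the named mirabegron reactions are at risk.* Mainly non-serious urinary infection is. Section 15 ties retention to bladder outlet obstruction and antimuscarinic use, and reports a controlled study in obstruction with no increase. Visit 3 says anticholinergics will not be prescribed.
- *A reader might infer a high infection rate under the stent.* The documents give none. Visit 3 supplies 10 days of ciprofloxacin, and the planned stent interval of 7 ± 3 days falls within that course when windows are kept.
- *A reader might infer that the wording favours one arm or hides a difference in pooled counts.* Staff are blinded, so the recorded fraction should be similar by arm. In the illustration above, filtering out every stent-period event would leave 5% v 10% visible; masking arises from pooling fully recorded events. Nor does Section 16C specify a pooled between-arm test.

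**Conclusion.** The point holds as an internal inconsistency that permits non-serious events to be filtered before recording, at the last on-drug contact and the only scheduled one after stent placement. Its likely effect is lower counts and a smaller absolute difference between arms, not a bias towards one arm. It concerns roughly 31 to 36 subjects, about 9 to 10 of them on mirabegron, if the plan's passage rates hold and all non-passers reach Visit 4. How many events would be lost cannot be estimated from the documents. The conclusion rests on staff following the visit text literally and on blinding holding. This is modest in size but worth correcting, because the edit is small and a missed event cannot be recovered at a later visit.

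The lack of a split by period in Section 16C is a separate and smaller point. It would remain after the Visit 4 sentence is corrected.

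**What to change.** **Section 9, Visit 4.** Delete the qualifier medication-related and name the checklist already used at Visits 2 and 3. Suggested sense: all adverse events since the previous contact are recorded on the checklist whatever their suspected cause, and the principal investigator then rates relatedness on the existing determination form. This brings the visit text into line with Appendix A and Section 16A. The cost is one phrase and a few more minor events to record, with no extra visit, test or staff.

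**Section 16C (separate addition).** Tabulate adverse events by arm for two periods: the expectant period (Visit 1 to Visit 2 or earlier surgery, all treated subjects) and the surgery/stent period (those who enter it). State in advance which table takes the interval from Visit 2 to Visit 3, which contains only subjects whose stone persisted. The expectant-period table keeps the randomised comparison. The stent-period table should be read as descriptive, because entry depends on the primary outcome. The cost is one sentence and one extra table, and the stent-period counts will be small.
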